8.3.6 Appropriateness of efficacy assessments

Efficacy measures in this study are primarily based on ESSDAI (EULAR SS Disease Activity Index) measuring organ-specific disease criteria, and on ESSPRI (European League Against Rheumatism [EULAR] Sjögren Syndrome [SS] Patient Reported Index) measuring the patient's subjective disease impact. Both instruments are widely accepted and validated, gold-standard measures of systemic and symptomatic manifestations of SjS, respectively.

ESSDAI is a systemic disease activity index that classifies disease activity in 3-4 levels, over each of 12 differentially weighted domains (biologic, hematologic, articular, glandular, cutaneous, constitutional, lymphadenopathy, renal, pulmonary, PNS, CNS and muscular). A composite weighted score provides an accurate assessment of disease activity, with a good sensitivity to change, as validated in multiple cohort studies ([Seror et al 2015](#)). The ESSPRI tool, on the other hand, is a patient reported composite score of symptoms of dryness, limb pain and fatigue evaluated on 0-10 visual analog scale, during the preceding 2 weeks ([Seror et al 2011](#)). Patient reported scores have poor sensitivity to change in disease activity, but among available tools, ESSPRI has been reported to have significantly better sensitivity. A recent prospective study reported poor correlation between systemic and patient scores, suggesting that the two indices evaluate complementary components of disease activity, therefore underscoring the importance of evaluation of both parameters to arrive at an accurate assessment of disease activity and change thereof ([Seror et al 2015](#)).

8.4 Safety

Safety assessments are specified below with the assessment schedule ([Table 8-1](#)) detailing when each assessment is to be performed.

For details on AE collection and reporting, refer to AE section.

The methods, assessment, specification, and recording for each assessment will be detailed in the SOM.

Table 8-2 Assessments and Specifications

Assessment	Specification
Physical	
A complete physical examination will include the examination of general appearance, skin, neck (including thyroid), eyes, ears, nose, throat, lungs, heart, abdomen, back, lymph nodes, extremities, vascular, and neurological. If indicated based on medical history and/or symptoms, rectal, external genitalia, breast, and/or pelvic exams may be performed.
 
The investigator should ask the patient for and pay attention to presence of signs and symptoms of infection.
 
Information for all physical examinations must be included in the source documentation at the study site. Clinically relevant findings that are present prior to signing informed consent must be recorded on the appropriate CRF that captures medical history. Significant findings made after signing informed consent which meet the definition of an Adverse Event must be recorded as an adverse event.

Vital signs	
Vital signs include blood pressure (BP) and pulse measurements. After the subject has been sitting for five minutes, with back supported and both feet placed on the floor, systolic and diastolic blood pressure will be measured using an automated validated device, with an appropriately sized cuff.
 
Clinically notable vital signs are defined in Section 16.1.

Height and weight	
Height in centimeters (cm) and body weight (to the nearest 0.1 kilogram (kg) in indoor clothing, but without shoes) will be measured.

Body Temperature	
Measured as per local default e.g. oral or ear/tympanic measurement.

The methods for each assessment and data recording details are specified in the SOM.

As per [Section 4.6](#), during a Public Health emergency as declared by Local or Regional authorities, i.e., pandemic, epidemic or natural disaster, that limits or prevents on-site study visits, regular phone or virtual calls can occur (every 4 weeks or more frequently if needed) for safety monitoring and discussion of the participant’s health status until it is safe for the participant to visit the site again.

8.4.1 Laboratory evaluations

A central laboratory will be used for analysis of all safety specimens collected. Details on the collection, shipment of samples and reporting of results by the central laboratory are provided to investigators in the central laboratory manual.

All abnormal lab results must be evaluated for criteria defining an adverse event but only reported as such if the criteria are met (please refer to [Section 10.1.1](#)). For those lab adverse events, repeated evaluations are mandatory until normalization of the result(s) or until the result is no longer considered to be clinically significant. Clinically notable laboratory findings are defined in [Section 16.1](#).

Table 8-3 Laboratory Evaluations

Test Category	Test Name
Hematology	Hemoglobin, Hematocrit, Mean Corpuscular Hemoglobin (MCH), Mean Corpuscular Hemoglobin Concentration (MCHC), Mean Corpuscular Volume (MCV), Red Blood Cells (RBC), White Blood Cells (WBC) plus differential count (Basophils, Eosinophils, Lymphocytes, Monocytes, Neutrophils, Bands), Platelets
Chemistry	Sodium, Potassium, Bicarbonate, Creatinine, Urea, Uric Acid, Chloride, Albumin, Calcium, Alkaline Phosphatase, total Bilirubin (if elevated above 1.5 times, direct and indirect Bilirubin will be differentiated), LDH, GGT, AST, ALT, Amylase, Lipase, CK, glucose, Total Cholesterol, Triglycerides; total Protein, Immunoglobulins quantitative (IgG, IgA, IgM, IgE); C-reactive Protein (CRP). Special clinical laboratory evaluations serum markers of B cell hyperactivity including but not limited to β 2-microglobulin, free immunoglobulin light chains and complement (C3, C4, CH50).
Urinalysis	Urinalysis: leucocytes, nitrite, pH, protein, glucose, ketones, urobilinogen, bilirubin, blood/hemoglobin. If positive for protein, nitrite, leucocytes and/or blood, sample will undergo microscopic analysis of WBC, RBC and casts.
Coagulation	Prothrombin time (PT), International normalized ratio [INR], Partial thromboplastin time (PTT), Activated partial thromboplastin time (APTT)
Serology	Hepatitis serology: hepatitis B surface antigen (HBsAg), hepatitis B core antibody (anti-HBc), HBV-DNA if applicable; hepatitis C virus antibody (HCVAb); HCV-RNA if applicable (see Section 8.1.1) Human immunodeficiency virus antibody (HIV Ab)
Hepatitis monitoring	HBsAg, HBV-DNA
Pregnancy Test	Serum / Urine pregnancy test (see Section 8.4.3)

8.4.2 Electrocardiogram (ECG)

Full details of all procedures relating to the ECG collection and reporting are contained in the technical manual provided by the core laboratory.

Standard 12-lead ECGs must be recorded after 10 minutes rest in the supine position according to the ECG investigator manual. See Section 1.2 of the SOM for recommendation on the ordering of assessments. The Fridericia QT correction formula (QTcF) should be used for clinical decisions.

Triplicate 12-lead ECGs are to be collected for central analysis as follows:

- Day 1: before administration of the first dose of study medication
- Week 4 and Week 24: before administration of study medication and 1h after administration of the study medication (study medication will be taken at the study site; ECG recording will be accompanied by taking samples for PK analysis (see [Section 8.5.3](#))).

Single 12-lead ECGs will be recorded at Screening, Week 2, Week 8, Week 12, Week 16, Week 20 and EOS.

For any ECGs with treatment emergent abnormalities, two additional ECGs must be performed to confirm the abnormal finding and copies forwarded to the central ECG laboratory for assessment. A monitoring or review process should be in place for clinically significant ECG findings throughout the study and especially at baseline before administration of study treatment.

In the event that a clinically significant ECG abnormality is identified at the site (eg severe arrhythmia, conduction abnormality of QTcF > 500 ms or QTcF prolongation > 60 ms), a copy of the assessment is sent to the core laboratory for expedited review if applicable, and the ECG is repeated to confirm the diagnosis. If the subject is hemodynamically compromised, the investigator or a medically qualified person must initiate appropriate safety procedures without delay (for example cardioversion).

Clinically significant abnormalities must be recorded on the eCRF as either medical history/current medical conditions or AEs as appropriate.

8.4.3 Pregnancy Commercially Confidential Information

All pre-menopausal women who are not surgically sterile will have pregnancy testing. Serum pregnancy test will be done at Screening and EOS and for remaining visits urine pregnancy test can be performed. Additional pregnancy testing might be performed if requested by local requirements. A positive urine test requires immediate interruption of study drug and needs to be confirmed with a serum test. If positive, the subject must be discontinued from the study treatment. Highly effective method of birth control must be used for women of child-bearing potential (see exclusion criteria definitions, [Section 5.2](#)).

If participants cannot visit the site to have pregnancy tests, urine pregnancy test kits may be used. Relevant participants can perform the urine pregnancy test at home and report the result to the site. It is important that participants are instructed to perform the urine pregnancy test first, and only if the test result is negative are they to proceed with administration of the study treatment. A communication process should be established with the participant so that the Site is informed and can verify the pregnancy test results (e.g., following country-specific measures).

Commercially Confidential Information

8.4.4 Appropriateness of safety measurements

The safety assessments selected are standard for this indication/subject population.

8.5 Additional assessments

Commercially Confidential Information

Commercially Confidential Information

Commercially Confidential Information

8.5.2 Other Assessments

Commercially Confidential Information

Commercially Confidential Information

8.5.3 Pharmacokinetics

PK samples will be collected at the visits and time points defined in the assessment schedule ([Table 8-1](#)). Follow instructions outlined in the laboratory manual regarding sample collection, numbering, processing and shipment.

Commercially Confidential Information

PK samples (blood) will be obtained in all subjects and at all dose levels. They will be evaluated in all subjects, except the placebo group.

Commercially Confidential Information

Concentrations will be expressed in mass per volume units (ng/mL) and will refer to the free base.

Commercially Confidential Information

For standard PK abbreviations and definitions see the list provided at the beginning of this protocol. The following PK parameters will be determined from the blood concentration time data using the actual recorded sampling times and non-compartmental method(s) with Phoenix WinNonlin (Version 6.4 or higher): C_{max}, T_{max}, AUC.

Commercially Confidential Information

The PK of LOU064 will be characterized at Week 4 and Week 24 across all treatment arms.

Commercially Confidential Information

Proposed sampling schedule and rationale is given in [Table 8-4](#). Detailed PK sampling schedule is given in [Table 8-1](#).

Table 8-4 PK sampling schedule

Time	Sample	Comment
Day 1	no PK assessment	Commercially Confidential Information
Week 4	Pre-dose, 0.5h/1h/2h/3h/4h/post-dose	Early Steady-state "full" PK profile baseline PK assessment, which allows synchronization of parallel cardiovascular investigations, which may be driven by initial high blood exposures (C _{max}) at the primary endpoint/interim analysis
Week 24 (last day, last dose)	Pre-dose, 0.5h/1h/2h/3h/4h/post-dose	Assess steady-state + intra-subject variability + putative time dependent effects on PK, CCI

9 Study discontinuation and completion

9.1 Discontinuation and completion

9.1.1 Study treatment discontinuation and study discontinuation

Discontinuation of study treatment for a subject occurs when study treatment is stopped earlier than the protocol planned duration and can be initiated by either the subject or the investigator.

The investigator must discontinue study treatment for a given subject if he/she believes that continuation would negatively impact the subject's well-being.

Study treatment must be discontinued under the following circumstances:

- Subject's decision
- Pregnancy

- Use of prohibited treatment as per recommendations in the prohibited treatment section ([Section 6.2.2](#))
- Any situation in which study participation might result in a safety risk to the subject, e.g. required surgical interventions associated with a risk of clinically significant bleeding
- Following emergency unblinding
- Emergence of the following AEs:
 - AEs including severe or serious hypersensitivity reactions for which continued exposure to the study drug would be detrimental
 - Abnormal liver laboratory results requiring discontinuation (see [Section 16.2](#))
 - Abnormal renal laboratory results requiring discontinuation (see [Section 16.3](#))
 - Platelets < 75 000/mm³
 - Any other laboratory abnormalities that in the judgment of the investigator, taking into consideration the subject's overall status, prevents the subject from continuing participation in the study
 - Patient received a live virus vaccination during the study

If discontinuation of study treatment occurs, the investigator should make a reasonable effort to understand the primary reason for the subject's premature discontinuation of study treatment and record this information.

Subjects who discontinue study treatment or who decide they do not wish to participate in the study further should NOT be considered withdrawn from the study UNLESS they withdraw their consent (see [Section 9.1.2](#)). **Where possible, they should return for the assessments** indicated in the assessment schedule ([Table 8-1](#)). If they fail to return for these assessments for unknown reasons, every effort (e.g. telephone, e-mail, letter) should be made to contact the subject/pre-designated contact as specified in the lost to follow-up section ([Section 9.1.3](#)). This contact should preferably be done according to the study visit schedule ([Table 8-1](#)).

If the subject cannot or is unwilling to attend any visit(s), the site staff should maintain regular telephone contact with the subject, or with a person pre-designated by the subject. This telephone contact should preferably be done according to the study visit schedule.

After study treatment discontinuation, at a minimum, in abbreviated visits, the following data should be collected at clinic visits or via telephone/email contact:

- New / concomitant treatments
- Adverse Events / Serious Adverse Events

The investigator must also contact the IRT to register the subject's discontinuation from study treatment.

If discontinuation occurs because treatment code has been broken, please refer to Emergency breaking of treatment code section (see [Section 6.6.3](#)).

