Personal Data	Subject information collected by the Investigator that is transferred to Novartis for the purpose of the clinical trial. This data includes subject identifier information, study information and biological samples
Premature subject withdrawal	Point/time when the subject exits from the study prior to the planned completion of all study drug administration and/or assessments; at this time all study drug administration is discontinued and no further assessments are planned
Randomization number	A unique identifier assigned to each randomized subject
Run-in Failure	A subject who is screened but not randomized/treated after the run-in period (where run-in period requires adjustment to subject's intervention or other treatment)
Screen Failure	A subject who did not meet one or more criteria that were required for participation in the study
Source Data/Document	Source data refers to the initial record, document, or primary location from where data comes. The data source can be a database, a dataset, a spreadsheet or even hard-coded data, such as paper or eSource
Start of the clinical trial	The start of the clinical trial is defined as the signature of the informed consent by the first subject
Study treatment	Any single drug or combination of drugs or intervention administered to the subject as part of the required study procedures
Study treatment discontinuation	When the subject permanently stops taking any of the study drug(s) prior to the defined study treatment completion date (if any) for any reason; may or may not also be the point/time of study discontinuation
Subject	A trial participant (can be a healthy volunteer or a patient)
Subject number	A unique number assigned to each subject upon signing the informed consent. This number is the definitive, unique identifier for the subject and should be used to identify the subject throughout the study for all data collected, sample labels, etc.
Treatment arm/group	A treatment arm/group defines the dose and regimen or the combination, and may consist of 1 or more cohorts
Variable	A measured value or assessed response that is determined in specific assessments and used in data analysis to evaluate the drug being tested in the study
Victim drug	The drug that is affected by the drug-drug interaction
Withdrawal of consent (WoC)	Withdrawal of consent from the study occurs only when a subject does not want to participate in the study any longer and does not allow any further collection of personal data

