16.1 Appendix 1: Clinically notable laboratory values and vital signs

The following specific criteria have been identified for this study. Should these criteria be met, a re-test should be done within 5 days after the first assessment based on investigator's clinical judgement. Discontinuation of the study treatment should be considered if the abnormal hematology parameter is confirmed:

Hemoglobin: < 10 g/dl

Platelets: < 75 000/mm³

White blood cells: 3 000/mm³

Neutrophils: < 1 500/mm³

For all other laboratory assessments, the central laboratory will flag laboratory values falling outside of the normal ranges on the central laboratory report (which the investigator should review and sign-off) and the investigator will report any values considered clinically significant in the eCRF.

Notable values for vital signs and change from baseline will be summarized.

Notable values are defined as follows: heart rate of < 50 and > 100 bpm; systolic blood pressure of < 90 and \geq 140 mmHg; diastolic blood pressure of < 60 and \geq 90 mmHg.

For ECGs a notable QTc value is defined as a QTc (Fridericia's) interval of greater than 450 msec for males or greater than 460 msec for females – all such ECGs will be flagged by the central CRO's cardiologist and require assessment for clinical relevance by the investigator.

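### Platelets below 75 000/mm³ force a treatment stop in Protocol 9.1.1, but Protocol 16.1 asks only that stopping be considered after a judgement-based re-test

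*Protocol*

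**What the plan says.** **Protocol 9.1.1** introduces its list with "Study treatment must be discontinued under the following circumstances". Under the sub-heading "Emergence of the following AEs" it gives "Platelets < 75 000" per mm³. No re-test or confirmation is attached. A separate item leaves any other laboratory abnormality to the investigator's judgement.

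**Protocol glossary** makes study treatment discontinuation a permanent stop: "When the subject permanently stops taking any of the study drug(s) prior to the defined study treatment completion date".

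**Protocol 16.1 (Appendix 1)** sets criteria for haemoglobin, platelets, white cells and neutrophils. The platelet value is again below 75 000/mm³. When a criterion is met, "a re-test should be done within 5 days after the first assessment based on" the investigator's clinical judgement. The next step is: "Discontinuation of the study treatment should be considered if the abnormal hematology parameter is confirmed". Nothing is said about dosing while the re-test is pending.

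**Protocol 9.1.4**, the study-level stopping rules, gives thrombocytopenia below the same figure as an example of a severe, drug-related event that rules out continued dosing. Two or more such events may put the study on hold.

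**The concern.** One laboratory value leads to two different instructions. An investigator who reads 9.1.1 stops treatment for good. One who reads 16.1 may re-test, may judge a re-test unnecessary, and may decide to continue after a confirmed low value. Following 16.1 as written can therefore breach 9.1.1 without the site noticing.

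What is at stake is patient safety and consistent conduct. Protocol 4.5 names impaired platelet function and cytopenia as risks that need close monitoring. Low-dose acetylsalicylic acid (5.2) and NSAIDs (6.2.3) are allowed during the study. Visits after Week 4 are about four weeks apart (Section 3), so a site that does not re-test may not see the patient again for some time. The conflict also leaves no single basis for deciding whether continued dosing was a protocol deviation.

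**Working it through.** No arithmetic model applies. The check sets the sections side by side.

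**1. Is it the same threshold?** Yes. 9.1.1 and 16.1 both use below 75 000/mm³. 9.1.4 uses the same figure per microlitre, which is the same unit (1 mm³ = 1 µL). Entry requires at least 100 000/µL (5.2, criterion 18). A patient eligible at screening must therefore have fallen by more than 100 000 − 75 000 = 25 000/µL to reach it.

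**2. Do the sections require the same action?** The four possible situations are:

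| Situation | 9.1.1 | 16.1 |
|---|---|---|
| Low value, investigator judges no re-test needed | Stop | No action on dosing |
| Low value, re-test pending (up to 5 days) | Stop | Silent on dosing |
| Low value confirmed | Stop | Consider stopping |
| Low value not confirmed | Stop (no confirmation step) | No action on dosing |

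16.1 does not require a stop in any of the four; 9.1.1 does in all four. The third row decides the matter. If 16.1 were only the confirmation step for 9.1.1, the two would agree once the value was confirmed, and they do not.

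**3. Does either section say which governs?** No. 9.1.1 refers to 6.2.2, 6.6.3, 9.1.2, 9.1.3, 16.2, 16.3 and Table 8-1, but not to 16.1. 16.1 refers to no other section. Of the three specific laboratory items in 9.1.1, liver and renal cite their appendices and platelets cites none: 2 of 3.

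**4. How many criteria are affected?** 16.1 has four haematology criteria. 9.1.1 makes one of them (platelets) a compulsory stop; 16.1 makes none compulsory. For haemoglobin, white cells and neutrophils 9.1.1 sets no threshold, so there is no conflict.

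**5. Which rule was meant?** Two things point to 9.1.1. First, it names platelets separately from the item that rests on judgement. Second, the cut-offs compare as follows:

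| Parameter | 9.1.1 | 16.1 | 9.1.4 |
|---|---|---|---|
| Platelets | < 75 000 | < 75 000 | < 75 000 |
| Haemoglobin (g/dl) | none | < 10 | < 8 |
| Neutrophils | none | < 1 500 | < 1 000 |
| White cells | none | 3 000 | none |

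For haemoglobin and neutrophils the alert value in 16.1 is milder than the value in 9.1.4. For platelets the two coincide, so the platelet entry in 16.1 already sits at the level that 9.1.4 associates with stopping. 9.1.4 is a study-level rule for drug-related events. It is evidence of intent and does not settle the individual case.

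**The case against.** The strongest reply is that the two sections can both be obeyed. 9.1.1 is the section on discontinuation, it is specific, and it is mandatory; 16.1 is a general appendix sentence covering four parameters. A site that stops and also re-tests satisfies both, and an instruction to consider stopping does not license ignoring a compulsory stop elsewhere. This is true, and it supports reading 9.1.1 as the governing rule. It does not remove the conflict, because the protocol never says so and 16.1 read alone gives a different result for a confirmed value.

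A second reply is that the general duties in 9.1.1 (stop if continuing would harm the subject, or in any safety-risk situation) apply from the first value. That limits the risk. The harm duty, however, depends on what the investigator believes, whereas the platelet rule is a fixed number.

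Some stronger readings are tempting but unsupported:

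- A reader might infer that 8.4.1 and 10.1.1 send sites to the weaker stopping rule. They do not. 8.4.1 says "Clinically notable laboratory findings are defined in" Section 16.1, and 10.1.1 points there for alert ranges. Both concern identifying abnormal values, not deciding on treatment.
- A reader might infer a parallel conflict for renal results, since 16.3 only asks that stopping be considered. The renal item in 9.1.1 cites 16.3 and reads naturally as covering results for which that assessment leads to discontinuation. No conflict is shown.
- A reader might infer from the adverse-event sub-heading that the number alone does not trigger the stop. 10.1.1 counts a laboratory value as an adverse event when it is considered clinically significant, and 9.1.4 gives this value as an example of such an event. The doubt is too weak to press.

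**Conclusion.** The point holds as a conflict between two safety instructions for one value, with no statement of precedence. It concerns one of four haematology criteria. The number of patients affected cannot be estimated, because the documents give no rate of thrombocytopenia. It deserves correction at the next amendment because it touches a stated stopping rule and costs little to settle.

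A reader might infer that the primary analysis is compromised. The documents do not support that: the estimand in Protocol 12.4.1 and SAP 1.2.1 uses data regardless of early termination or treatment interruption, and no stated figure changes.

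The conclusion assumes that no text outside the visible documents reconciles the sections. Material after 10.2.2 is redacted, and the central laboratory manual and Site Operations Manual are not available. No redaction is visible in 16.1 or in the 9.1.1 list itself. What sites would actually do is not known.

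**What to change.** In 16.1, take platelets out of the sentence that asks for discontinuation to be considered, and add: *Platelets < 75 000/mm³: study treatment must be discontinued per Section 9.1.1.* In 9.1.1, add *(see Section 16.1)* to the platelet item. Leave the re-test wording and the haemoglobin, white cell and neutrophil criteria as they are. There is no need to make the re-test obligatory: 8.4.1 already requires repeat tests for laboratory values that count as adverse events.

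If the sponsor prefers to guard against a spurious single value, it should write one alternative rule identically in both sections: interrupt dosing at the first value and discontinue permanently if it is confirmed. Section 8.4.3 already uses this pattern for a positive urine pregnancy test. That choice is a safety decision for the sponsor and would relax the present 9.1.1 rule.

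The cost is a small wording amendment. Under the main version a single unconfirmed low value ends treatment for good, but 9.1.1 already has that effect.
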